1.2.1.3 Safety Profile[20]

At the time of the study-specific data cutoff dates, 893 subjects have received talmogene laherparepvec (with doses from 10^4 to 10^8 PFU/mL) and have provided safety data across 15 studies. Thirty-one of these subjects continued into the extension phase of 2 of these studies. Overall, most adverse events reported in subjects administered talmogene laherparepvec are non-serious and primarily include flu-like symptoms and injection site reactions. Most fatal adverse events reported in subjects administered talmogene laherparepvec were reported in the setting of disease progression.

Table 1.2.1.3 Adverse Reactions Observed in Imlygic Clinical Trials

ADRs are displayed by MedDRA SOC, PT and frequency in the Imlygic arm using the following convention: very common ($\geq 1/10$); common ($\geq 1/1,000$ to $< 1/100$); rare ($\geq 1/10,000$ to $1/1,000$); very rare ($< 1/10,000$).

		Imlygic (N= 292)			
System Organ Class Preferred Term	CIOMS Frequency	Events with Severity			
		All Events n (%)	Grade 3-4 n (%)	Grade 5 n (%)	Serious Events n (%)
Number of Subjects reporting treatment-emergent adverse events	Very Common	290 (99.3)	94 (32.2)	11 (3.8)	75 (25.7)
Infections and Infestations					
Cellulitis	Common	17 (5.8)	6 (2.1)	0 (0)	7 (2.4)
Oral herpes	Common	14 (4.8)	0 (0)	0 (0)	0 (0)
Incision site infection	Uncommon	2 (<1)	0 (0)	0 (0)	0 (0)
Neoplasms benign, malignant and unspecified (Incl cysts and polyps)					
Tumour pain	Common	22 (7.5)	5 (1.7)	0 (0)	4 (1.4)
Infected neoplasm	Common	8 (2.7)	3 (1.0)	0 (0)	3 (1.0)
Plasmacytoma ¹	Uncommon	1 (<1)	1 (<1)	0 (0)	1 (<1)
Blood and lymphatic system disorders					
Anaemia	Common	15 (5.1)	3 (1.0)	0 (0)	2 (<1)
Immune system disorders					
Glomerulonephritis	Uncommon	1 (<1)	1 (<1)	0 (0)	1 (<1)
Pneumonitis ²	Uncommon	1 (<1)	1 (<1)	0 (0)	0 (0)
Psoriasis ³	Uncommon	1 (<1)	1 (<1)	0 (0)	0 (0)
Vasculitis	Uncommon	1 (<1)	0 (0)	0 (0)	0 (0)
Metabolism and nutrition disorders					
Dehydration	Common	12 (4.1)	5 (1.7)	0 (0)	2 (<1)
Nervous system disorders					
Headache	Very Common	55 (18.8)	2 (<1)	0 (0)	0 (0)
Dizziness	Common	28 (9.6)	0 (0)	0 (0)	0 (0)
Eye disorders					
Keratitis herpetic	Uncommon	1 (<1)	0 (0)	0 (0)	0 (0)
Vascular disorders					
Flushing	Common	11 (3.8)	0 (0)	0 (0)	0 (0)
Deep vein thrombosis	Common	6 (2.1)	5 (1.7)	0 (0)	3 (1.0)
Respiratory, thoracic and mediastinal disorders					
Oropharyngeal pain	Common	17 (5.8)	0 (0)	0 (0)	0 (0)
Obstructive airways disorder	Uncommon	1 (<1)	1 (<1)	0 (0)	1 (<1)
Gastrointestinal disorders					
Nausea	Very Common	104 (35.6)	1 (<1)	0 (0)	0 (0)
Vomiting	Very Common	62 (21.2)	5 (1.7)	0 (0)	2 (<1)
Diarrhoea	Very Common	55 (18.8)	1 (<1)	0 (0)	0 (0)
Constipation	Very Common	34 (11.6)	0 (0)	0 (0)	2 (<1)
Abdominal pain	Common	26 (8.9)	3 (1.0)	0 (0)	0 (0)
Abdominal discomfort	Common	6 (2.1)	0 (0)	0 (0)	0 (0)
Skin and subcutaneous tissue disorders					
Rash	Common	26 (8.9)	1 (<1)	0 (0)	0 (0)
Vitiligo	Common	15 (5.1)	0 (0)	0 (0)	0 (0)
Dermatitis	Common	5 (1.7)	0 (0)	0 (0)	0 (0)
Musculoskeletal and connective tissue disorders					
Myalgia	Very Common	51 (17.5)	1 (<1)	0 (0)	0 (0)
Arthralgia	Very Common	50 (17.1)	2 (<1)	0 (0)	0 (0)
Pain in extremity	Very Common	48 (16.4)	4 (1.4)	0 (0)	0 (0)
Groin pain	Common	10 (3.4)	0 (0)	0 (0)	0 (0)

General disorders and administration site conditions					
Fatigue	Very Common	147 (50.3)	5 (1.7)	0 (0)	0 (0)
Chills	Very Common	142 (48.6)	0 (0)	0 (0)	1 (<1)
Pyrexia	Very Common	125 (42.8)	0 (0)	0 (0)	5 (1.7)
Injection site reactions ⁴	Very Common	115 (39.4)	3 (1.0)	0 (0)	0 (0)
Influenza like illness	Very Common	89 (30.5)	2 (<1)	0 (0)	1 (<1)
Malaise	Common	12 (4.1)	0 (0)	0 (0)	0 (0)
Axillary pain	Common	10 (3.4)	0 (0)	0 (0)	0 (0)
Investigations					
Weight decreased	Common	17 (5.8)	1 (<1)	0 (0)	0 (0)
Injury, poisoning and procedural complications					
Contusion	Common	14 (4.8)	0 (0)	0 (0)	0 (0)
Procedural pain	Common	9 (3.1)	1 (<1)	0 (0)	1 (<1)
Wound complication	Common	4 (1.4)	0 (0)	0 (0)	0 (0)
Wound secretion	Common	4 (1.4)	0 (0)	0 (0)	0 (0)

Adverse events were coded using MedDRA version 15.1.

Adverse Reactions were defined as: adverse events with $\geq 2\%$ more frequent incidence in Imlygic-treated patients compared to GM-CSF-treated patients in Study 1 OR adverse events with less than 2% difference, but with a biologically plausible mechanism and similar in medical concept to other adverse events.

The classification of Very common, Common and Uncommon events is based on cutoff percentages that were applied to adverse event incidence in the "All Events" column of the Imlygic arm.

1 Plasmacytoma at the injection site.

2 Pneumonitis is considered an immune mediated event and is therefore categorized with the other adverse events in the system organ class of Immune system disorders.

3 Worsening psoriasis.

4 Injection Site Reactions includes Injection site pain, Injection site erythema, Injection site haemorrhage, Injection site swelling, Injection site reaction, Injection site inflammation, Secretion discharge, Injection site discharge, Injection site warmth.

Important Identified Risks[20]

- Disseminated herpetic infection in severely immunocompromised individuals (those with any severe congenital or acquired cellular and/or humoral immune deficiency).
- Accidental exposure of healthcare providers to talimogene laherparepvec.
- Obstructive airway disorder.
- Immune-mediated adverse events.
- Plasmacytoma at the injection site.
- Deep vein thrombosis
- Cellulitis at site of injection.
- SCCHN Indication: Arterial Bleeding (Carotid Artery Blowout Syndrome).

Important Potential Risks[20]

- Disseminated herpetic infection in immunocompromised patients (such as those with human immunodeficiency virus [HIV]/acquired immunodeficiency syndrome [AIDS], leukemia, lymphoma, common variable immunodeficiency, or those who require high-dose steroids or other immunosuppressive agents).
- Symptomatic talimogene laherparepvec infection in non-tumor tissue in treated patients.
- Transmission of talimogene laherparepvec from patient to close contacts or HCPs via direct contact with injected lesions or body fluids resulting in symptomatic infection (primary or reactivation).

- Symptomatic herpetic infection due to latency and reactivation of talimogene laherparepvec or wild-type HSV-1 in patients.
- Combination with other therapies like chemotherapy or immunosuppressive agents.
- Recombination of talimogene laherparepvec with wild-type HSV-1 virus may occur.
- Impaired wound healing at site of injection.
- Delayed next line treatment in non-responders.
- Loss of efficacy in patients treated with systemic acyclovir for complications.
- Talimogene laherparepvec-mediated anti-GM-CSF antibody response.

1.2.1.4 Special Warning and Precautions for Use

Immunocompromised Patients

Talimogene laherparepvec has not been studied in immunocompromised patients. Based on animal data, patients who are severely immunocompromised may be at an increased risk of disseminated herpetic infection and should not be treated with talimogene laherparepvec. Disseminated herpetic infection may also occur in immunocompromised patients (such as those with HIV/AIDS, leukemia, lymphoma, common variable immunodeficiency, or who require chronic high-dose steroids or other immunosuppressive agents). Consider the risks and benefits of treatment before administering talimogene laherparepvec to these patients.

Accidental Exposure to TVEC

Accidental exposure may lead to transmission of talimogene laherparepvec and herpetic infection. Healthcare providers, close contacts (household members, caregivers, sex partners, or persons sharing the same bed), pregnant women, and neonates should avoid direct contact with injected lesions or body fluids of treated patients. Accidental needle stick and splash back have been reported in healthcare providers during preparation and administration of talimogene laherparepvec.

Patients should be advised to avoid touching or scratching injection sites as this could lead to inadvertent transfer of Imlrylic to other areas of their body. Close contacts who are pregnant or immunocompromised should not change the patient's dressings or clean their injection sites.

Caregivers should be advised to wear protective gloves when assisting patients in applying or changing occlusive dressings and observe safety precautions for disposal of used dressings and cleaning materials.

In the event of an accidental exposure to talimogene laherparepvec, exposed individuals should be advised to clean affected area thoroughly with soap and water and/or a disinfectant. If signs or symptoms of herpetic infection develop, they should contact their healthcare provider. Talimogene laherparepvec is sensitive to acyclovir.

Herpetic Infection in TVEC-treated Patients

In clinical studies, herpetic infections (including cold sores and herpes keratitis) have been reported in patients treated with talimogene laherparepvec. Patients who develop herpetic infections should be advised to follow standard hygienic practices to prevent viral transmission. Talimogene laherparepvec is sensitive to acyclovir. Consider the risks and benefits of talimogene laherparepvec treatment before administering acyclovir or other anti-viral agents indicated for management of herpetic infection. These agents may interfere with the effectiveness of talimogene laherparepvec.

Cellulitis at the Injection Site

Necrosis or ulceration of tumor tissue may occur during talimogene laherparepvec treatment. Cellulitis and systemic bacterial infection have been reported. Careful wound care and infection precautions are recommended, particularly if tissue necrosis results in open wounds.

Immune-mediated Events

In clinical studies, immune-mediated events including glomerulonephritis, vasculitis, pneumonitis, worsening psoriasis, and vitiligo have been reported in patients treated with talimogene laherparepvec.

Plasmacytoma at the Injection Site

Plasmacytoma has been reported in proximity to the injection site after administration of talimogene laherparepvec. Consider the risks and benefits of talimogene laherparepvec in patients with multiple myeloma or in whom plasmacytoma develops during treatment.

Obstructive Airway Disorder

Obstructive airway disorder has been reported following talimogene laherparepvec treatment. Use caution when injecting lesions close to major airways.

Arterial Bleeding (Carotid Artery Blowout Syndrome)

Fatal carotid arterial bleeding (carotid blowout syndrome) has been reported following administration of talimogene laherparepvec in the squamous cell carcinoma of the head and neck (SCCHN) setting. Subjects with tumor(s) in direct contact or encasing a major blood vessel, ulceration and/or fungation onto the skin surface, and subjects with history of re-irradiation for SCCHN or prior lymph node neck dissection may be at increased risk for arterial bleeding if talimogene laherparepvec is injected into a tumor located near a major blood vessel. Such high risk subjects should not be administered talimogene laherparepvec in the SCCHN setting.

1.3 Study Rationale

The overall goal of this phase I trial is to exploit the oncolytic and immune-stimulating properties of talimogene laherparepvec to develop a new therapeutic approach to human peritoneal surface dissemination of gastrointestinal, fallopian tube, ovarian, and primary peritoneal cancers. As an exploratory endpoint, we will evaluate the impact of talimogene laherparepvec on peritoneal leukocyte populations of patients with peritoneal surface malignancies. We hope to set the stage for future clinical trials by evaluating the safety of intraperitoneal delivery of talimogene laherparepvec to patients who cannot undergo complete cytoreductive surgery for peritoneal surface dissemination of gastrointestinal, fallopian tube, ovarian or primary peritoneal malignancies.

2.0 OBJECTIVES

2.1 Primary Objective

The primary objective of this trial is:

1. To evaluate the toxicity profile of intraperitoneal talimogene laherparepvec in patients with peritoneal surface dissemination from gastrointestinal, fallopian tube, ovarian, or primary peritoneal tumors.

2.2 Secondary Objectives

The secondary objective of this trial is:

1. To evaluate the pharmacokinetic profile and viral shedding of talimogene laherparepvec by measuring viral load in plasma and urine as well as viral load in peritoneal fluid.

2.3 Exploratory Objectives

The exploratory objectives of this trial are:

1. To evaluate the magnitude and duration of tumor response.
2. To evaluate the time to tumor progression as measured by radiographic imaging, clinical symptoms, and/or tumor marker levels.
3. To describe the clinical activity of talimogene laherparepvec, as measured by overall survival.
4. To evaluate the changes in peritoneal cavity leukocyte populations after the treatment of peritoneal surface dissemination of gastrointestinal, fallopian tube, ovarian, and primary peritoneal cancers with talimogene laherparepvec.

3.0 STUDY DESIGN

3.1 Study Description

This is a non-randomized, open-label Phase I trial in patients with Stage IV peritoneal surface dissemination from gastrointestinal, fallopian tube, ovarian, or primary peritoneal tumors enrolled at Duke Cancer Institute and select external collaborating institutions. All subjects will complete an extensive medical history, baseline physical examination and clinical assessment to ensure subject eligibility requirements (see Eligibility Criteria for details) within 4 weeks of starting study drug. All eligible patients must have a peritoneal catheter placed prior to the initiation of therapy. All patients will receive an initial seroconversion dose of talimogene laherparepvec 4×10^6 PFU on Cycle 1 Day 1 to enable seroconversion as described in the currently approved treatment protocol for the treatment of cutaneous melanoma. Three weeks (+3 days) after the initial seroconversion dose, patients will receive talimogene laherparepvec at the dose level for the cohort for which they are enrolled every 2 weeks (± 3 days) for up to 4 doses. The length of the first cycle is 5 weeks and subsequent cycles are 2 weeks in duration.

- Enrolled subjects are defined as subjects who give informed consent.
- Screen failures are defined as subjects who give informed consent and do not meet eligibility criteria.
- Accrued subjects are defined as subjects who give informed consent and meet eligibility criteria.
 - Withdrawal: Subject accrued but later withdrawn from the study, either before or after receiving a study drug.
 - Evaluable: In the Dose Escalation Cohort, subjects who are accrued, received study treatment, and completed the first cycle of safety assessments or have dose limiting toxicity (DLT) which is study treatment related that precludes completing the full cycle of assessments will be considered evaluable for DLT. All subjects (in Dose Escalation and Dose Expansion) who are accrued and receive any study treatment will be considered evaluable for toxicity. All subjects in Dose Escalation and Dose Expansion who are accrued and receive any study treatment will be considered evaluable for efficacy.
 - Non-evaluable: In the Dose Escalation Cohort, subjects who accrued but did not complete the first cycle of safety assessments due to reasons other than study treatment-

related toxicity (e.g. disease progression or inter-current illness) are considered non-evaluable for DLT. All subjects (in Dose Escalation and Dose Expansion) who are accrued, received study treatment but did not complete initial restaging due to reasons other than disease progression (e.g. inter-current illness) will be considered non-evaluable for efficacy.

Table 3.1 Proposed Dose Levels

Dose Level	No. Evaluable Subjects	TVEC IP, once every 2 weeks x 4 doses*
Dose Escalation		
1 (starting dose)	3-6	4×10^6
2	3-6	4×10^7
3	3-6	4×10^8
Dose Expansion		
Expanded Cohort	6	MTD

*All patients will receive an initial seroconversion dose of 4×10^6 PFU. The first dose at each of these Dose Levels will be administered 3 weeks (+3 days) after the initial seroconversion dose, and then be given every 2 weeks \pm 3 days for a total of 4 doses at each Dose Level (in addition to the initial seroconversion dose, which all patients will receive).

Using a standard '3+3' dose escalation design, there are up to three dose levels that may be explored. See Table 3.1 for the dosing scheme.

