All patients will receive an initial seroconversion dose of intraperitoneal talimogene laherparepvec 4×10^6 PFU on Cycle 1 Day 1 to enable seroconversion as described in the currently approved treatment protocol for the treatment of cutaneous melanoma. Three weeks after the initial seroconversion dose, patients will receive talimogene laherparepvec at the dose level for the cohort for which they are enrolled every 2 weeks for up to 4 doses (in addition to the initial seroconversion dose, which all patients will receive). The length of the first cycle is 5 weeks and subsequent cycles are 2 weeks in duration.

In the Dose Escalation Cohort, three subjects will be enrolled at the starting dose of 4×10^6 PFU, and the dosing will continue in the standard '3+3' dose escalation scheme. If the starting dose is tolerated, enrollment will continue at 4×10^7 and 4×10^8 PFU. Once the MTD is determined, six subjects will be enrolled to the Dose Expansion Cohort at the MTD. All subjects will be dosed with talimogene laherparepvec IP once every 2 weeks for up to 4 doses (in addition to the initial seroconversion dose, which all patients will receive).

Study Assessments

Safety: Toxicity and safety assessments will be performed weekly during the 5 weeks, then every 2 weeks for up to 4 treatment visits. These assessments will include vital signs, ECOG performance status, medical history, physical examination, complete blood count (CBC), biochemistry, creatinine, AST, ALT, and bilirubin. Toxicities will be recorded using National Cancer Institute Common Terminology Criteria for Adverse Events (NCI-CTCAE) version 5.0. General symptom management and supportive care will be provided as clinically indicated to ensure optimal patient care. After discontinuation of study treatment, subjects will have toxicity and safety assessments 30 days after last dose of study drug.

Tumor Assessments

Restaging scans and blood tumor markers will be repeated at the end of cycle 4, after receipt of the fifth dose of study drug. Tumor response will be assessed using treating physician's discretion, based on a composite of RECIST 1.1 measurements, blood tumor markers (CEA or CA-125), measurements of abdominal girth, and/or clinical response.

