5.1 Screening Period

During the Screening Period, subjects are consented and screened for the study. Informed consent must be obtained before initiation of any screening procedure that is performed solely for the purpose of determining eligibility for this study. Evaluations performed as part of routine care before informed consent can be considered as screening evaluations if done within the defined screening period, and if permitted by the local Institutional Review Board (IRB) / Independent Ethics Committee (IEC) policies. Study eligibility is based on meeting all of the inclusion criteria and none of the exclusion criteria (refer to [Section 4.0](#)) before the first dose of study drug on Cycle 1 Day 1.

The following study procedures must be done within 28 days prior to Cycle 1 Day 1:

- Demographics
- Medical and cancer history
- Concomitant medications
- Physical examination
- Abdominal measurement
- Height
- Vital signs and weight
- ECOG performance status
- Adverse event assessment (review of baseline symptoms)
- Tumor assessment (CT and/or MRI scans)
- Blood tumor marker, if clinically indicated (e.g., CEA or CA19-9)
- Whole blood (for pharmacogenomics) (may be collected pre-dose on Cycle 1 Day 1)
- Coagulation tests (must be done prior to catheter placement)
- Peritoneal catheter placement (must be placed after confirmation of eligibility)

The following study procedures must be done within 7 days prior to Cycle 1 Day 1:

- CBC with differential
- Chemistries including liver function tests (LFTs)
- Serum pregnancy test (only for women of childbearing potential)

Subject eligibility is determined using lab results obtained prior to peritoneal port placement and up to 7 days prior to Cycle 1 Day 1. The Screening Period ends upon placement of the peritoneal port or final determination that the subject is ineligible for the study. Patients with pre-existing peritoneal ports for standard of care treatment are eligible for participation. For these patients the Screening Period ends upon receipt of the first dose of study drug or final determination that the subject is ineligible for the study.

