6.2.2 Administration

All eligible subjects will have a Bard peritoneal catheter placed prior to the initiation of therapy. Talimogene laherparepvec will be administered via intraperitoneal (IP) administration. The planned dose of talimogene laherparepvec (measured as plaque forming units or PFU) will be delivered in a 500 mL volume of normal saline. After the infusion, patient should roll to the right side, wait 10 minutes, then roll to the left side and wait an additional 10 minutes, and repeat this procedure of rolling to the right side and the left side every 10-15 minutes to ensure exposure of the virus to the peritoneal surfaces where disease is located. Patients will have vital signs (blood pressure, pulse, temperature, and respiratory rate) taken every 15 minutes for the first hour after infusion, then remain under observation for an additional hour to ensure no significant toxicity is endured as a result of the administration. At the end of the second hour, vitals should be taken again prior to discharge. This procedure should be repeated each of the 5 potential times that talimogene laherparepvec is administered throughout the course of the study.

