7.1 Dose Modifications

Subjects experiencing one or more AEs due to the study drug may require dose modification(s) as described in Table 7.1. If talimogene laherparepvec treatment was delayed by > 1 week, that dose will be deemed to have been missed and the subject will proceed to the next scheduled treatment visit. Missed doses will not be made up. If talimogene laherparepvec dosing is delayed by more than 4 weeks from the date of the planned dose (i.e., approximately 6 weeks from the previous dose) due to the occurrence of an adverse event that is considered related to talimogene laherparepvec, the subject must be permanently taken off talimogene laherparepvec treatment. If talimogene laherparepvec is delayed by more than 4 weeks from the date of the planned dose (i.e., approximately 6 weeks from the previous dose) for reasons other than treatment-related toxicity, the case must be reviewed by the PI to determine if the subject can resume talimogene laherparepvec therapy.

Table 7.1 Talimogene Laherparepvec Dose Modifications

HEMATOLOGIC ADVERSE EVENTS		
Toxicity Grade ^a	Occurrence	Talimogene Laherparepvec
NEUTROPENIA		
Grade 1	Any	Maintain dose
Grade 2	Any	Maintain dose
Grade 3($\geq 0.5 - < 1 \times 10^9/L$)	1 st	Hold until grade ≤ 1 , then resume at current dose
	2 nd and higher	Hold until grade ≤ 1 , then resume at 80% of current dose ^d
Grade 4 ($< 0.5 \times 10^9/L$)	1 st	Hold until grade ≤ 1 , then resume at 80% of current dose. ^{b,c,d}
	2 nd and higher	Hold until grade ≤ 1 , obtain permission of PI to resume at 60% of current dose ^d
FEBRILE NEUTROPENIA		
Grade 3 (neutropenia and fever $\geq 38.5C$)	1 st – 2 nd	Hold until resolution of fever and neutropenia to grade ≤ 1 , then resume at 60% of current dose ^d
	3 rd	Discontinue Protocol Therapy
Grade 4 (neutropenia and fever $> 38.5 C$)	Any	Discontinue Protocol Therapy

- a. National Cancer Institute Common Terminology Criteria Version 3.0
- b. Continued treatment only if it is considered to be in the best interest of the patient
- c. Consider growth factor support if continuing treatment is felt to be in the patient's best interest.

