Management of any toxicity related to talimogene laherparepvec administration or study may involve holding therapy until patients have recovered from any talimogene laherparepvec- or study-related adverse events. The management of the above known and other toxicity not listed above is largely based upon supportive care and institutional standards in managing these conditions. The management is at the discretion of the treating physician. If deemed appropriate, the treating physician may seek out subspecialty medical care of the patients, e.g. ophthalmologic evaluation for suspected herpetic keratitis, dermatologic consult for skin lesions that need specialist evaluation, or infectious disease consult for suspected herpes infections. Supportive medications may be employed at the discretion of the treating physician to support a patient through symptoms experienced as a result of the toxicity, e.g. pain medications for pain, anti-diarrheal agents for diarrhea, stool softeners and laxatives for constipation, anti-pyretics for fevers, intravenous and oral fluids for dehydration and dizziness, etc. Should a treating physician have any questions about how to treat symptoms related to talimogene laherparepvec or the study, he or she should be encouraged to speak with the PI or co-PI for guidance.

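### Section 3.1 can be read to count a level 2 or 3 subject as DLT-free at the end of cycle 1 when only the 4×10^6 PFU seroconversion dose was given

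*Combined protocol and SAP*

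**What the plan says.** **Who is evaluable.** Section 3.1 defines as evaluable for DLT "subjects who are accrued, received study treatment, and completed the first cycle of safety assessments", and also subjects whose treatment-related DLT stops them completing the cycle. A subject is non-evaluable for DLT only if cycle 1 assessments were not completed for some other reason. Missing the cohort-level dose is not listed as a ground.

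**When the level is first given.** Every cohort receives 4×10^6 PFU on Cycle 1 Day 1. The footnote to Table 3.1 states: "The first dose at each of these Dose Levels will be administered 3 weeks (+3 days) after the initial seroconversion dose". Cycle 1 lasts 5 weeks, so it contains one cohort-level dose, on Day 22.

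**What happens to a late dose.** Under Section 7.1, if a dose is delayed by more than a week, "that dose will be deemed to have been missed and the subject will proceed to the next scheduled treatment visit". It adds: "Missed doses will not be made up".

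**Status of the Day 1 dose.** Section 5.1 sets the deadline for eligibility as "before the first dose of study drug on Cycle 1 Day 1". The synopsis places restaging "after receipt of the fifth dose of study drug", a total that includes Day 1. Section 6.2.2 likewise refers to "each of the 5 potential times that talimogene laherparepvec is administered".

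**The decision.** Under Section 3.2, subjects are watched for the first 5 weeks before advancement. A level passes with 0 DLTs in 3 subjects or 1 in 6.

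**The concern.** At level 1 the seroconversion dose equals the cohort dose, so the definition does no harm there. At levels 2 and 3 the cohort dose is 10 and 100 times the seroconversion dose. A DLT-free subject who has had only the seroconversion dose by the end of cycle 1 says nothing about the level being judged, yet can fill one of its 3 to 6 evaluable places and count as a pass.

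Two decisions are exposed: the tenfold step from level 2 to level 3, and the first acceptance of level 3. Each rests on very few subjects, so one uninformative pass matters. The effect is not one-way in every case, because a related DLT after the seroconversion dose counts against the level. The concern is confined to unexposed subjects without a DLT.

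**Working it through.** **1. Timeline in cycle 1 (35 days; Sections 3.1 and 7.1)**

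- Cohort dose on Day 22: 35 − 21 = 14 days of observation at the level.
- Cohort dose 7 days late, on Day 29: 35 − 28 = 7 days.
- Delay of more than 7 days: the dose is missed. The next treatment visit is Cycle 2 Day 1 = Day 36, so there are 0 days at the level within cycle 1. The subject stays on study and can complete the Day 8, 15, 22 and 29 assessments.

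**2. Can the Day 22 dose be missed without a DLT?** Yes, by several routes.

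- Table 7.1 holds drug for Grade 3 or 4 neutropenia, whereas the only neutropenia listed as a DLT in Section 3.2.1 is febrile.
- Section 3.2.1 excludes Grade 3 fatigue of any duration from DLT, while Section 7.2 says management may involve "holding therapy until patients have recovered from any talimogene laherparepvec- or study-related adverse events".
- Section 7.1 also provides for delays unrelated to treatment toxicity.

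**3. Does other text close the gap?** Sections 3.2, 9.1 and 10.5 contain no minimum-exposure or replacement rule. The window in Section 3.2.1 (during treatment and up to 30 days after the last injection) governs which events count, not which subjects are evaluable.

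**4. Size.** The plan gives no operating characteristics for its 3+3 rule, so there is no figure to reproduce. Assumptions, none of them from the documents: true DLT rate p at the level, per-subject miss probability m, and zero DLT risk in an unexposed subject unless stated.

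With q the DLT probability per counted subject,

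P(pass) = (1−q)^3 + 3q(1−q)^2 × (1−q)^3.

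*All exposed, p = 0.40:* 0.216 + (3 × 0.40 × 0.36) × 0.216 = 0.216 + 0.093 = 0.309.

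*Misses counted as DLT-free:* q = p(1−m). At p = 0.40 and m = 5%, q = 0.38: 0.238 + 0.438 × 0.238 = 0.343.

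*Exactly one of the first three unexposed, any further three exposed:* (1−p)^2 + 2p(1−p) × (1−p)^3. At p = 0.40: 0.36 + 0.48 × 0.216 = 0.464.

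| p | All exposed | m = 5% | m = 10% | m = 20% | One of first three unexposed |
|---|---|---|---|---|---|
| 0.30 | 0.494 | 0.525 | 0.557 | 0.622 | 0.634 |
| 0.40 | 0.309 | 0.343 | 0.378 | 0.454 | 0.464 |
| 0.50 | 0.172 | 0.202 | 0.234 | 0.309 | 0.313 |

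If the seroconversion dose itself carries an assumed 5% DLT risk, the 0.464 becomes 0.36 × 0.95 + (0.48 × 0.95 + 0.36 × 0.05) × 0.216 = 0.444.

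The last column is conditional on a miss having happened. At m = 5%, the chance that at least one of the first three is unexposed is 1 − 0.95^3 = 0.14.

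**The case against.** **The text can be read the other way.** In Section 3.1 the toxicity and efficacy definitions refer to *any* study treatment, and the DLT definition omits that word. The places that count the Day 1 dose speak of study drug or name the product. Section 5.8 counts study treatment in cycles after the seroconversion dose. Table 3.1 ties evaluable subjects to each level's dose. Section 5.3 and Appendix C list Day 22 procedures that presuppose an infusion. This makes the wording ambiguous, but it does not settle it. The Day 1 dose falls within the Treatment Period and is called the first dose of study drug, non-evaluability turns only on incomplete assessments, and Appendix C footnote 19 ties the post-infusion vital signs to days when drug is given.

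**Exposure is late, not absent.** This stands. Unless the subject discontinues, Section 7.1 sends them to the next treatment visit, about Day 36, for the cohort dose. Related DLTs then still count under Section 3.2.1, and the rule of 33% or more in Section 3.2 applies to any dose level.

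**The team would notice.** The trial is open-label, Section 3.2 calls its rules guidelines, and the lead investigator monitors adverse events continuously. Excluding such a subject by judgement is plausible, but no rule requires it.

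**The size is assumed.** This also stands. The documents give no rate of missed Day 22 doses, holding drug under Section 7.2 is discretionary, and most Grade 3 non-hematologic toxicity lasting more than 3 days is itself a DLT.

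**Conclusion.** The point holds in a limited form. Section 3.1 states who is evaluable without requiring the cohort-level dose. Together with the missed-dose rule in Section 7.1, it can be read to count a level 2 or 3 subject as DLT-free at the end of cycle 1 after 4×10^6 PFU only. The decisions affected are escalation from level 2 to level 3 and the first acceptance of level 3.

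A reader might infer that such subjects never receive the level's dose, or that the MTD will be set too high. The documents do not support either. The cohort dose normally follows at about Day 36, later related DLTs still count, up to 6 subjects are treated at the MTD, and 6 more follow in expansion. The calculation describes the week-5 decision only.

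The frequency is unknown and may be low. With an assumed 40% DLT rate and zero risk if unexposed, the average shift in the chance of passing is 0.31 to 0.34 at an assumed 5% miss rate. It is 0.31 to 0.46 (0.44 if the seroconversion dose carries a 5% risk) in a cohort where one of the first three is in fact unexposed. That is enough to justify a cheap wording change.

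**What to change.** Add to the DLT-evaluability definition in Section 3.1:

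- A subject without a DLT is evaluable for DLT only if the first dose at the assigned level was given in cycle 1 and the cycle 1 follow-up after it was completed.
- Subjects who miss that dose for reasons other than a treatment-related DLT are replaced.
- Every treatment-related DLT, including one before Day 22, stays in the level's count. The change therefore cannot remove observed toxicity.

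**Cost.** An occasional replacement subject, each adding about 5 weeks before the cohort decision. Over the up to 12 evaluable subjects at levels 2 and 3, expected replacements are 12m/(1−m): 0.6/0.95 = 0.63 at an assumed 5% miss rate and 1.2/0.90 = 1.33 at 10%. Table 3.1 already counts evaluable subjects. The room between the synopsis maximum of 24 evaluable and the 30 treated allowed in Section 9.1 is 6, which must also cover subjects who are already non-evaluable under the present definition.
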